8.5.1 Monitoring the Study

The responsible study monitor or Sponsor's designee will contact and visit the Investigator as necessary, and he/she will be allowed, upon request, to inspect and verify all records of the study (e.g., source document, ICFs, CRFs, regulatory documents) in a manner consistent with GCP and all other applicable state and federal law.

It will be the study monitor's responsibility to inspect the source documents to verify the adherence to the protocol and the completeness, consistency, and accuracy of the data being entered in the CRF. The monitor will verify that each subject has consented in writing prior to any study procedures being performed. Where the terms of the Informed Consent, GCP, and all other applicable state and federal law permit, the monitor should have access to laboratory test reports and other subject records needed to verify the entries on the CRF. The Investigator (or his/her designee) agrees to cooperate with the monitor to ensure that any issues detected in the course of these monitoring visits are resolved.

In addition, the Sponsor's internal auditors (or designee) and government inspectors may evaluate the study and must be allowed access to CRFs, source documents, and other study files.

The Investigator must notify the Sponsor (or designee) promptly of any inspections of the study or activities related to the study scheduled by regulatory authorities, allow the Sponsor (or designee) to be present, and promptly forward copies of inspection reports to the Sponsor (or designee).

8.6 Reporting for the Study

8.6.1 Case Report Forms

Celerion standard CRFs will be supplied. CRFs are produced, stored electronically, and are available to the designated study team members. Each CRF is reviewed and signed by the Investigator. The final signed CRFs are provided to the Sponsor in the format as decided upon between Celerion and the Sponsor (e.g., compact disc, flash drive, secure file transfer protocol). This will be documented in the Data Management Plan (if applicable).

8.6.2 Data Coding

AEs will be coded using MedDRA[®]. Concomitant medications will be coded using the World Health Organization Drug Dictionary. Each dictionary version will remain the same throughout the trial. Coding will be completed by qualified members of the Celerion staff.

8.6.3 Report Format

According to the ICH Harmonised Tripartite Guideline (Organization of the Common Technical Document for the Registration of Pharmaceuticals for Human Use M4 and the ICH M2 Expert Working Group), the final report will be written according to the ICH E3 Guideline (Structure and Content of Clinical Study Reports).

8.6.4 Record Keeping

All raw data generated in connection with this study, together with the original copy of the final report, will be retained by Celerion until at least 5 years after the last approval of a marketing application in an ICH region and until there are no pending or contemplated marketing applications in an ICH region or at least 5 years have elapsed since the formal discontinuation of clinical development of the investigational product. These documents should be retained for a longer period however if required by the applicable regulatory requirements or by an agreement with the sponsor. It is the responsibility of the Sponsor to inform the Investigator/Institution as to when these documents no longer need to be retained.

8.7 Publication Policy

All unpublished information given to Celerion by the Sponsor shall not be published or disclosed to a third party without the prior written consent of the Sponsor.

The data generated by this study are considered confidential information and the property of the Sponsor. This confidential information may be published only in collaboration with participating personnel from the Sponsor or upon Sponsor's written consent to publish the information.

10. APPENDICES

- Appendix 1. Demographics Questionnaire
- Appendix 2. Urge to Smoke Questionnaire
- Appendix 3. Product Evaluation Scale (PES)
- Appendix 4. Intent to Use Questionnaire

Appendix 1: Demographics Questionnaires**Screening Demographics Questionnaire**

1. What is your date of birth?

2. What is your sex?

Male

Female

3. Which one of these groups would you say best describes your race?

White/Caucasian

Black/African American

Asian

Native Hawaiian or other Pacific Islander

American Indian or Alaska Native

Other (SPECIFY): _____

4. Are you Hispanic or Latino?

Yes

[figure not shown]
No

Appendix 2: Urge to Smoke Questionnaire

Note: The following question will be paired with a VAS. The VAS will be anchored with “Not at All” on the left and “A great deal” on the right.

Please respond to the question by making a vertical mark anywhere along the horizontal line.

Right now, how much would you like to smoke a cigarette?

Appendix 3: Product Evaluation Scale (PES)

(Hatsukami 2013)

Please mark the number that best represents how using the product made you feel.

1. Was it satisfying?
2. Did it taste good?
3. Did you enjoy the sensations in your mouth?
4. Did it calm you down?
5. Did it make you feel more awake?
6. Did it make you feel less irritable?
7. Did it help you concentrate?
8. Did it reduce your hunger for food?
9. Did it make you dizzy?
10. Did it make you nauseous?
11. Did it immediately relieve your craving for a cigarette?
12. Did you enjoy it?
13. Did it relieve withdrawal symptoms?
14. Did it relieve the urge to smoke?
15. Was it enough nicotine?
16. Was it too much nicotine?
17. Was it easy to use?
18. Were there bothersome side effects?
19. Were you comfortable using the product in public?
20. Did you still have a craving for a cigarette after using the product?
21. Are you concerned that you would become dependent on this product?

Scale: 1 = not at all, 2 = very little, 3 = a little, 4 = moderately, 5 = a lot, 6 = quite a lot, 7 = extremely

Four multi-item subscales will be derived from "Satisfaction" (items 1, 2, 3, and 12); "Psychological Reward" (items 4 through 8); "Aversion" (items 9, 10, 16, and 18); and "Relief" (items 11, 13, 14, 15, and reversed for item 20) and single items 17, 19, and 21 will be summarised.

Appendix 4: Intent to Use Questionnaire

Note: The following question will be paired with a VAS. The VAS will be anchored with “Not at All” on the left and “Extremely” on the right.

Please respond to each phrase by making a vertical mark anywhere along the horizontal line.

1. If available, how likely are you to buy and use your assigned study product in the future?

# 1. INTRODUCTION

The following statistical analysis plan (SAP) provides the framework for the analysis and presentation of the data from this study. Any changes made from the planned analysis described in the protocol or after finalization of this SAP will be documented in the Clinical Study Report (CSR). The section referred to as "Table, Figure, and Listing Shells" within this SAP describes the Clinical Data Interchange Standards Consortium (CDISC) input in order to provide traceability to the corresponding tables, figures, and listings (TFLs). Analysis data model (ADaM) is the source for tables and figures (as well as listings that may contain derived data) and study data tabulation model (SDTM) is the source for the data listings.

Any additional exploratory analyses not addressed within this SAP and/or driven by the data, or requested by Imperial Brands PLC will be considered out of scope and must be described in the CSR.

# 2. OBJECTIVES AND ENDPOINTS

# 2.1 Objectives

#### Primary

1. To evaluate and compare the maximum plasma nicotine concentration (Cmax) and the area under the plasma nicotine concentration-time curve at the last time point measured (AUCt) following controlled use of each Heated Tobacco Product (HTP), Heated Herbal Product (HHP), or cigarette comparator.

#### Secondary

- 1. To evaluate other pharmacokinetic (PK) parameters of nicotine after the controlled use of each HTP, HHP, or cigarette comparator.
- 2. To evaluate the change in smoking urges observed after the controlled use of each HTP, HHP, or cigarette comparator.
- 3. To evaluate product perception and preference using subjective assessments.
- 4. To evaluate the tolerability and safety of each of the products used.
- 5. To investigate usage behaviour for each product using measurements of topography parameters (puff count, puff duration, puff volume, peak puff flow rate, average puff flow rate, inter puff interval) for each product following *ad libitum* product use sessions.

## 2.2 Study Endpoints Including Key Assessments and Summarization

Pharmacokinetics:

For each morning product use session on Days 1 through 5, plasma nicotine PK parameters (AUCinf, AUC0-90, AUC0-240, AUCt, Cmax, Clast, Tmax, T1/2) will be computed from the individual plasma concentrations for each study product. Baseline adjustments will be performed.

Nicotine concentrations and PK parameters will be listed by subject and summarised using descriptive statistics.

#### Subjective Effects:

#### Intent to Use (ITU)

Descriptive statistics of the visual analogue scale (VAS) will be provided by study product and product use session. Individual responses will be listed by subject.

#### Urge to Smoke

Responses and derived parameters (Emax, TEmax, AUEC0-240) will be listed by subject and summarised using descriptive statistics.

#### Product Evaluation Scale

Responses will be considered as a 7-point scale, and will be presented as factors outlined in Section 9.2.

Descriptive statistics of the subscales will be provided by study product and product use session. Individual responses will be listed.

#### Puff Topography:

Puff topography will be assessed using a SPA-M topography device. Since the device collects topography data for approximately 60 minutes, it will need to reset at 60 minutes in order to collect 2 hours of topography data. Topography parameters (puff count, puff duration, puff volume, peak puff flow rate, average flow rate, inter-puff interval) will be listed by subject and summarised using descriptive statistics.

#### Product Use Behaviour:

All product use data, including the number HTP/HHP sticks used and the number of Subject's own brand combustible cigarettes (OBCCs) smoked (Days -1 through Day 5), will be summarised using descriptive statistics.

Incidence of device malfunction(s) will also be tabulated.

#### Safety:

Safety will be monitored in-study through physical examination (symptom-driven), vital signs measurements, electrocardiogram (ECGs), and clinical laboratory tests (serum chemistry, haematology, and urinalysis).

Adverse events (AEs) spontaneously reported by the subjects or observed by the Investigator or other study personnel will be monitored from Screening until the follow-up.

AEs will be tabulated and summary statistics for vital signs and clinical laboratory tests may be computed and provided, as deemed clinically appropriate.

# 3. STUDY DESIGN

This study is designed to meet the objectives outlined in Section 2.1.

This will be a randomised, cross-over, open-label, confinement study conducted in 25 adult male or female smokers of combustible cigarettes. The study will investigate OBCC, HTPs, and HHPs, in a cross-over design, incorporating PK evaluation, subjective effects assessments, usage behaviour, and puff topography. The study will also incorporate a product use safety evaluation.

Subjects will perform a Screening Visit and 1 Study Visit, including a 6-day confinement period and finally a follow-up telephone call approximately 7 days after the final study product use.

#### Visit 1 (Screening)

Screening procedures will be performed within 28 days prior to study procedures on Day -1 and will include an eligibility check, review of health status and assessment of nicotine consumption habits. Medical and tobacco-use histories and demographic data will be collected. Other screening procedures include a physical examination (including oral cavity and oropharynx), vital signs, ECG, body mass index (BMI), clinical laboratory tests (haematology, serum chemistry, urinalysis), serology, urine/saliva drug, urine/breath alcohol, cotinine screen, exhaled carbon monoxide (CO), and pregnancy and follicle-stimulating hormone (FSH) tests (for females as appropriate). If required, subjects will be offered smoking cessation advice and contact information for a smoking cessation support service.

#### Visit 2 (In-clinic period, Day -1 to Day 5)

At Visit 2, subjects who successfully complete the screening procedures and meet all the inclusion criteria and none of the exclusion criteria will be eligible to check in to the clinical research unit (CRU) on Day -1 and will remain at the clinic until Day 5 for daily study

product use, PK sampling, subjective questionnaire assessments, puff topography (as applicable), and safety assessments.

On Day -1, following eligibility confirmation, subjects will undertake a familiarisation session of the study products and questionnaires. The clinical team will explain how the HTPs and HHPs will be used. Subjects will have the opportunity to see the products/devices and packaging and will participate in a Product Trial where they will take 5 puffs on a single one HTP stick (flavour chosen by subject) and 5 puffs on a single HHP stick (flavour chosen by subject). All products/devices used in the trial session will not be used in the clinical study but will be retained as demonstration samples for accountability purposes. An explanation of how the questionnaires will be administered to the subjects will be given. After the familiarisation session and completion of check-in procedures, subjects will be allowed to smoke their own cigarettes *ad libitum* but will abstain from use of any tobacco- or nicotine-containing products for at least 12 hours prior to the start of the morning controlled product use session on Day 1.

In the morning of Days 1 through 5, after pre-use assessments and confirmation of eligibility, subjects will use their randomly-assigned study product under controlled conditions by completely using a single unit (one stick, approximately 10 puffs) of the assigned study product, with puffs taken at 30-second intervals and of 3-second duration. PK samples will be collected within 5 minutes pre-study product use (timepoint '0') and at 2, 4, 6, 8, 10, 15, 30, 45, 60, 120, and 240 minutes following the start of study product use. Questionnaires will be administered to the subject at defined intervals throughout the day. Safety will be monitored throughout the day.

On Days 1 through 5, following the 4-hour PK blood collection, subjects will start a 4-hour *ad libitum* product use session (no limits on cigarette, HTP or HHP consumption) with the same study product used during the morning controlled use session.

On Days 1 through 5, puff topography will be performed over the last 2-hour period during the 4-hour *ad libitum* product use session. The Sodim Smoking Puff Analyzer Mobile (SPA-M) topography device will collect data (puff count, puff duration, puff volume, peak puff flow rate, average puff flow rate, inter-puff interval) for 2 hours. The SPA-M topography device will be reset at 60 minutes in order to collect 2 hours of data.

The *ad libitum* product use session on Days 1 through 5 will start at approximately the same time each day, with lunch served at the start of the *ad libitum* product use session, at approximately the same time each day. After completion of the *ad libitum* use session, subjects will be allowed to smoke their own cigarettes (*ad libitum*) but will abstain from use of any tobacco- or nicotine-containing products for at least 12 hours prior to the start of the morning controlled product use scheduled on the following day.

A new/unused device will be provided to the subjects on each day of HTP/HHP use (i.e., the same device will be used for the morning controlled product use and *ad libitum* product use sessions on the same day).

On Day 5, following completion of study assessments, subjects will be allowed to smoke their own cigarettes and will leave the CRU after completing all final check out requirements.

# Visit 3 (Follow-up telephone call)

A follow-up telephone call (Visit 3) will be made by the CRU in an attempt to contact all subjects who used at least one study product (including subjects who terminate the study early) using their standard procedures approximately 7 days after the final product use to determine if any AE has occurred since the last study visit.

Subjects will not be forced to use any tobacco/nicotine products at any time during the study.

## 4. SAMPLE SIZE ESTIMATION

The sample size chosen for this study was selected without statistical considerations. It has been determined adequate to meet the study objectives.

#### 5. SUBJECT RANDOMISATION

Subjects who complete the study screening assessments and meet all the eligibility criteria and are randomised will be assigned a unique randomisation identification number on Day -1 and will receive study products according to the randomisation scheme.

The sequences to be used in the randomisation will be ABECD, BCADE, CDBEA, DECAB, and EADBC, with 5 subjects randomly assigned to each sequence.

#### 6. ANALYSIS POPULATIONS

Safety Population will include all subjects who have successfully completed eligibility requirements after checking in to the CRU and used at least one study product.

Outcomes Population will include a subset of the safety population and will consist of subjects who used a study product and have evaluable PK, subjective effects, or topography data. This population will be used in the summary and analysis of PK, subjective effects, topography, and product use, and all available data will be included in the summary tables to the extent possible.

#### 7. STUDY PRODUCT DESCRIPTIONS

All subjects will use Products A through E

The following products will be tested in this study:

# 8. PHARMACOKINETIC ANALYSIS

#### 8.1 Measurements and Collection Schedule

On each of Days 1 through 5, venous blood samples (~4 mL per sample) for plasma nicotine analysis will be collected within 5 minutes pre-study product use (timepoint '0') and at 2, 4, 6, 8, 10, 15, 30, 45, 60, 120, and 240 minutes following the start of controlled study product use .

#### 8.2 Bioanalytical Method

Plasma nicotine will be analysed by LC-MS/MS at Celerion Bioanalytical Services Lincoln, Nebraska, using validated analytical methods with appropriate quality controls according to the Food and Drug Administration (FDA) Guidance for Industry (Title 21 CFR Part 58). Additionally, processing of samples will completed by a non-tobacco user.

#### 8.3 Pharmacokinetic Concentrations

For the concentration tables, unadjusted plasma nicotine concentrations that are below the limit of quantification (BLQ) will be set to one-half of the lower limit of quantitation for the calculation of descriptive statistics.

Individual nicotine concentrations will be adjusted for baseline nicotine ("baseline-adjusted") and all PK parameters will be calculated based on the adjusted concentrations. Baseline adjustment will be performed by subtraction of the pre-existing nicotine concentration from

each nicotine concentration obtained after test product administration in that period/day for each subject using the following equation:

 $C_t = C_t \text{ unadjusted} - [C_0 \cdot e^{-Kel \cdot t1}]$ 

where Ct is the adjusted concentration at time t, Ct unadjusted is the observed concentration at time t, C0 is the pre-product use concentration (-5 minutes),  $K_{el} = \frac{\ln(2)}{T^{1/2}}$ , T1/2 is 2 hours (average nicotine half-life), t is the actual sampling time since product administration, and t1 is the actual sampling time since the time of the pre-product use sample.

After correction for pre-product administration values, some concentrations may be BLQ and some may be negative values. Negative values will be assigned a value of zero in the analyses and all other values obtained will be reported as is even if these values are BLQ.

Baseline-adjusted plasma nicotine concentrations will be used for the calculation of the plasma nicotine PK parameters.

All concentration data will be included in the calculation of the individual PK parameters, the individual concentration-time plots (based on actual sample times), and in the mean concentration-time plots (based on nominal sample times). However, if there are any significant deviations from nominal sample times, some concentration data may be excluded from the descriptive statistics and the mean concentration-time plots and/or additional concentration-time plots of the mean data may be provided. All deviations and excluded data will be listed and discussed in the CSR.

# 8.4 Noncompartmental Pharmacokinetic Analysis and Parameter Calculation

The appropriate noncompartmental PK parameters will be calculated from the baselineadjusted plasma nicotine concentration-time data using Phoenix® WinNonlin® Version 8.1 or higher. Actual sample times will be used in the calculations of the PK parameters. The calculation of the actual time for plasma nicotine will be in respect to the start of product use. All PK parameters included in the protocol are listed in Table 8.1 below, and are defined as appropriate for study design.

Parameter	Label to be Used in the Text, Tables and Figures	Definition	Method of Determination
AUC 0-90	AUC0-90	Area under the baseline-adjusted nicotine concentration-time curve from time zero (defined as the start of the product use session) to the 90-minutes time point.	Calculated using the Linear Trapezoidal with Linear Interpolation Method
		If the 90-minutes plasma concentration is missing, BLQ, or not reportable, then interpolation and/or extrapolation will be conducted, as appropriate. If interpolation and/or extrapolation cannot be reliably performed, then this parameter cannot be calculated.	
AUC 0-240	AUC0-240	Area under the baseline-adjusted nicotine concentration-time curve from time zero (defined as the start of the product use session) to the to the 240-minutes time point. If the 240-minutes plasma concentration is missing, BLQ, or not reportable, then interpolation and/or extrapolation will be conducted, as appropriate. If interpolation and/or extrapolation cannot be reliably performed, then this parameter cannot be calculated.	Calculated using the Linear Trapezoidal with Linear Interpolation Method
AUCt	AUCt	Area under the baseline-adjusted nicotine concentration-time curve from time zero (defined as the start of the product use session) to the time of the last measurable non-zero concentration.	Calculated using the Linear Trapezoidal with Linear Interpolation Method
AUC inf	AUCinf	Area under the baseline-adjusted concentration-time curve from time 0 extrapolated to infinity	Calculated as: $AUC_t + (C_{last}/ K_{el})$ where $C_{last}$ is the last observed/measured concentration

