| T _{max} | Time to reach the maximum baseline-adjusted plasma concentration. If the maximum value occurs at more than one time point, T _{max} is defined as the first time point with this value. |
| T _{1/2} | Terminal elimination half-life. |

Plasma concentrations below the limit of quantitation will be set to one-half of the lower limit of quantitation for the calculation of descriptive statistics of unadjusted plasma nicotine concentrations and for the calculation of baseline-adjusted nicotine concentrations.

Nicotine concentrations and PK parameters will be listed by subject and summarised by study product, by sex and overall using descriptive statistics.

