## Note: Plasma Nicotine Concentration Tables (CPCONC1) will have the following format:

Page 1 of X

Unadjusted Plasma Nicotine Concentrations (ng/mL) Following Controlled Product Use of iD Balanced Blue Stick (Outcomes Population)

Subject Number	Product Sequence	Study Period	Sex	Pre-use	XX	XX	Samp XX	ole Times XX	(minutes) XX	XX	XX	XX	XX	XX
XX XX XX XX	XXXXXX XXXXXX XXXXXX	X X X	XX XX XX	XX XX XX XX	XX XX XX	XX XX XX	XX XX XX XX	XX XX XX	XX XX XX	XX XX XX	XX XX XX	XX XX XX	XX XX XX	XX XX XX
n Mean SD CV(%) SEM Minimum Median Maximum			Male**	X X.X X.XX XX.X XX.X X.XX XX XX XX	X X.X X.XX XX.X XX.X X.XX XX X.X XX XX	X X.X X.XX XX.X XX.X X.XX XX X.X X.X XX	X X.X X.XX XX.X X.XX X.XX XX X.X XX	X X.X X.XX XX.X XX.X XX XX XX XX XX	X X.X X.XX XX.X XX.X XX XX X.X XX XX	X X.X X.XX XX.X XX.X XX XX XX XX XX XX	X X.X X.XX XX.X XX.X X.XX XX X.X XX XX	X X.X X.XX XX.X XX.X X.XX XX X.X XX XX	X X.X X.XX XX.X XX.X X.XX XX X.X XX X.X	X X.X X.XX XX.X XX.X XX X.XX XX XX XX

Program: /CAXXXX/sas prg/pksas/PROGRAMNAME.SAS DDMMMYYYY HH:MM

Programming Notes: Footnotes to include under the table, as appropriate:

<. = Concentration value missing or not reportable.>

The following footnote will only be included in the unadjusted plasma nicotine tables: < For the calculation of summary statistics, values that are below the limit of quantitation (BLQ) of <XX> are treated as 1/2 LLQQ.>

\*\*There will also be summary statistics for female and overall

The following footnote will only be included in the baseline-adjusted plasma nicotine tables: < Prior to baseline adjustment, concentration values that are below the limit of quantitation (BLQ) of <XX> were set to 1/2 the LLQQ. After baseline adjustment, any negative values were assigned a value of zero and all other values obtained were reported as is (even if lower than the original limit of quantitation of <xx> ng/mL) for the calculation of the descriptive statistics.> For baseline-adjusted table, Pre-use will be replaced with 0.

Concentrations will be presented to same precision as in bioanalytical data.

Summary statistics presentation with respect to the precision of the bioanalytical data: n = integer; Mean and Median +1; SD and SEM +2, Min and Max +0, CV% to 1 decimal.

PK Time points are: pre-use and 2, 4, 6, 8, 10, 15, 30, 45, 60, 120 and 240 minutes following the start of product use.

Program:	/CAXXXXX/sas_prg/pksas/pk-conc-tables.sas	DDMMYYYY	HH:MM
Program:	/CAXXXXX/sas_prg/pksas/pk-conc-tables-sig.sas	DDMMYYYY	HH:MM

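### SAP Table 8.1 treats a BLQ 240-minute concentration as missing when AUC0-240 is computed, although SAP 8.3 and Protocol 7.3.1 give that sample a usable value

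*SAP*

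**What the plan says.** The AUC0-240 row of SAP Table 8.1 (section 8.4) reads: "If the 240-minutes plasma concentration is missing, BLQ, or not reportable, then interpolation and/or extrapolation will be conducted, as appropriate". It continues: "If interpolation and/or extrapolation cannot be reliably performed, then this parameter cannot be calculated". The method column gives the linear trapezoid with linear interpolation and names no extrapolation method.

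SAP 8.3 handles low values differently. After baseline adjustment, "Negative values will be assigned a value of zero in the analyses", while "all other values obtained will be reported as is even if these values are BLQ". It also states: "All concentration data will be included in the calculation of the individual PK parameters".

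For raw values below the LLOQ, Protocol 7.3.1 prescribes half the LLOQ for the descriptive statistics of unadjusted concentrations "and for the calculation of baseline-adjusted nicotine concentrations". The footnote to the SAP concentration-table shell (CPCONC1) agrees: before adjustment, such values "were set to 1/2 the LLQQ" (the shell's spelling).

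Protocol 7.3.1 defines AUC0-240 as a linear trapezoid to the 240-minute point, with no BLQ exception. SAP section 13 declares no departure from the protocol. The schedule in SAP 8.1 ends with samples at "10, 15, 30, 45, 60, 120, and 240 minutes following the start of controlled study product use".

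**The concern.** One sample is subject to two incompatible rules. Under SAP 8.3 and Protocol 7.3.1, a BLQ sample at 240 minutes always has a number. Under Table 8.1 that number is set aside and the sample is handled as if it had never been drawn. A BLQ result still carries information, because it says the concentration was low. Replacing it by a prediction from earlier points discards that information, and declaring the area not calculable discards the whole profile for this parameter.

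A low 4-hour value is more common when a product delivers little nicotine. The set of profiles contributing to AUC0-240, and the value used for each, could therefore depend on delivery. Two analysts following different sentences of the SAP could also produce different AUC0-240 tables from the same data.

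**Working it through.** The documents state no AUC figure, power or LLOQ to reproduce. The conflict is shown from the text; its size can only be illustrated.

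**1. The rules side by side, for the 240-minute sample**

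| Situation | SAP 8.3 with Protocol 7.3.1 | SAP Table 8.1, AUC0-240 row |
|---|---|---|
| Raw value below LLOQ | Half the LLOQ, then adjusted; zero if negative | Extrapolate, or do not calculate |
| Raw value above LLOQ, adjusted value below it | Adjusted value kept; zero if negative | Same as above if BLQ means the adjusted value; otherwise kept |
| Missing or not reportable | No value | Extrapolate, or do not calculate |

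The SAP does not say which meaning of BLQ applies in Table 8.1.

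**2. The value that SAP 8.3 supplies**

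The baseline term is C0 × exp(−Kel × t1), with a half-life of 120 min. With the pre-use sample at −5 min, t1 = 245 min and the factor is exp(−ln 2 × 245/120) = 0.243. If the pre-use and 240-minute samples are both raw BLQ, the kept value is LLOQ/2 × (1 − 0.243) = 0.379 × LLOQ.

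**3. What replacement changes**

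The last trapezoid is (240 − 120)/2 × (C120 + C240). Replacing C240 therefore changes AUC0-240 by 60 × (extrapolated − kept) ng·min/mL.

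Two assumed profiles, both with LLOQ 1.0 and pre-use 2.0 ng/mL:

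- Raw 240-minute value 0.745, so BLQ on either reading. The kept value is 0.5 − 2.0 × 0.243 = 0.014. AUC0-240 is 137.3 with the kept value and 150.4 with extrapolation. The difference of 13.1 (+9.5%) corresponds to an extrapolated value of 13.1/60 + 0.014 ≈ 0.23.
- Raw value 1.185, adjusted 1.185 − 0.486 = 0.699, so BLQ on the adjusted reading only. AUC0-240 is 230.4 kept and 230.6 extrapolated (+0.1%).

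**4. How often**

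All inputs here are assumptions:

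- 4,000 simulated profiles per setting at the planned times.
- Geometric mean Cmax 2, 5, 10 or 15 ng/mL and median pre-use level 1.5 ng/mL, both with log-SD 0.6.
- Median half-life 120 min (log-SD 0.25) and 8% assay error.
- LLOQ 0.2, 0.5 or 1.0 ng/mL.
- Extrapolation as C120 × exp(−Kel × 120), with Kel from the 45, 60 and 120 min points.
- AUC0-240 counted as lost if the Kel criteria in SAP 8.4 fail.

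Results at mean Cmax 2 / 5 / 10 / 15 ng/mL:

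| LLOQ | Adjusted value below LLOQ (%) | Raw value below LLOQ (%) | AUC0-240 lost, adjusted reading (%) |
|---|---|---|---|
| 0.2 | 38 / 13 / 4 / 2 | 2.6 / 0.3 / 0.1 / 0.0 | 12.5 / 2.6 / 0.5 / 0.1 |
| 0.5 | 72 / 38 / 14 / 6 | 30 / 11 / 2 / 1 | 24.4 / 6.8 / 1.1 / 0.3 |
| 1.0 | 76 / 68 / 37 / 21 | 60 / 44 / 19 / 9 | 29.2 / 14.7 / 3.8 / 1.3 |

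Where both rules give a value, the median change is about 0 to +1%. The 5th to 95th percentile range at mean Cmax 2 is −7 to +7%, −9 to +10% and −16 to +11% for the three LLOQs. At mean Cmax 15 it is about −5 to +7% at most. Separately, the SAP 8.4 rule requiring three consecutive quantifiable points removes 0.5% to 18.5% of profiles from every parameter at mean Cmax 2.

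**The case against.** The strongest reply is that Table 8.1 leaves room for judgement and may do little in practice. Extrapolation is to be done as appropriate, and the parameter is withheld only if extrapolation is not reliable, a term the SAP does not define. When Kel is not calculated, SAP 8.4 withholds T1/2, AUCinf and AUC%extrap; AUC0-240 is not on that list. The Kel criteria concern the shape and fit of the profile, not low concentration, so the SAP does not say that weak profiles lose AUC0-240. One could even read the BLQ wording as dormant, since SAP 8.3 has already assigned values. Any loss would also be visible, because SAP 8.5 reports n and lists excluded parameter data.

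Much of this stands. The loss percentages depend on equating Kel failure with unreliable extrapolation. The dormant reading, however, appears nowhere in the text; Table 8.1 names BLQ as a trigger in its own right.

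It may also be said that actual times are used with a ±3 minute window (Protocol 6.4.1), so a draw just after 240 minutes permits interpolation. It does, but only by using that same low sample, which is what Table 8.1 sets aside.

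A reader might infer that the rule flatters the weakest product. The documents do not identify a low-delivery product, and where a value survives the change can go either way. A reader might also cap the change at 60 × LLOQ. That bounds only the area contributed by a kept value below LLOQ. With LLOQ 0.5, a kept value of 0 and an extrapolated value of 1.0, the change is 60 ng·min/mL, not 30.

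**Conclusion.** The contradiction holds on the text alone and needs no assumption. Followed as written, Table 8.1 can replace a usable low measurement with a prediction or leave AUC0-240 uncalculated. The rule is triggered more often when delivery is low, on either meaning of BLQ and at every LLOQ tried.

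The size is not determined by the documents, which give no LLOQ and no expected Cmax. The loss of 12.5% to 29.2% at mean Cmax 2 ng/mL, against 0.1% to 1.3% at 15 ng/mL, is conditional on the assumed profiles, the adjusted reading of BLQ and the Kel-failure assumption. Selective loss matters more than alteration of the values that remain.

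Two wider inferences are not supported. The primary comparison is unaffected: SAP 8.6 analyses Cmax and AUCt, and AUC0-240 is a secondary parameter summarised descriptively. The AUC0-90 row carries the same wording but not the same problem: no 90-minute sample is planned, so that area is already interpolated between 60 and 120 minutes.

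Severity: minor.

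**What to change.** In the AUC0-240 row of SAP Table 8.1, delete BLQ from the trigger. State that the baseline-adjusted concentration is used at 240 minutes, with raw BLQ values set to half the LLOQ before adjustment (Protocol 7.3.1) and negative adjusted values set to zero. Restrict extrapolation to a 240-minute sample that is missing or not reportable. AUC0-90 needs no change.

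The cost is a sentence or two in the SAP before database lock, with no new data. The row would then agree with the protocol's plain trapezoid to 240 minutes. The downside is that a few AUC0-240 values will rest on half the LLOQ or zero at the last point, which the protocol and SAP 8.3 already accept.
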